2.1.6 Pharmacodynamic [REDACTED] endpoints

Blood biomarkers (Eotaxin-3, serum total IgE, Thymus and Activation-Regulated Chemokine [TARC] and periostin) will all be assayed at Visit 2(Week 0), Visit 8 (Week 24) and Visit 10 (Week 52).

Urine biomarkers (Leukotriene E4 and a metabolite of prostaglandin D2 (PGDM)) will be measured in morning spot urine samples using validated quantitative assays.

[REDACTED]

2.1.6.1 [REDACTED]

[REDACTED]

[REDACTED]

[REDACTED]

[REDACTED]

2.1.7 Health Related Quality-of-life endpoints

2.1.7.1 Euro-QOL-5D

The European quality of life-5D scale (EQ-5D) ([Appendix E](#)) is a standardized HRQoL questionnaire developed by the EuroQol Group in order to provide a simple, generic measure of health for clinical and economic appraisal (11). EQ-5D is designed for self-completion by patients.

The EQ-5D essentially consists of 2 pages: the EQ-5D descriptive system and the EQ VAS. The EQ-5D comprises 5 dimensions: mobility, self-care, usual activities, pain/discomfort and anxiety/depression. Each dimension has 5 levels: no problems, slight problems, moderate problems, severe problems, and extreme problems. The EQ VAS records the respondent's self-rated health on a vertical VAS. The EQ VAS 'thermometer' has endpoints of 100 (best imaginable health state) at the top and 0 (worst imaginable health state) at the bottom. EQ-5D self-reported VAS data generates information on the self-perceived overall health-related quality of life.

EQ-5D will be assessed at Visit 2 (Week 0), Visit 7 (Week 16), Visit 8 (Week 24), Visit 9 (Week 40) and Visit 10 (Week 52).

2.1.8 Health economic endpoints

A questionnaire of health care resource utilization (reliever medication, specialist visit, hospitalization, emergency or urgent medical care facility visit, outcome, sick leaves, school days loss, etc) will be administered at Visit 2 (Week 0), Visit 7 (Week 16), Visit 8 (Week 24), Visit 9 (Week 40) and Visit 10 (Week 52).

2.2 DISPOSITION OF PATIENTS

This section describes patient disposition for both patient study status and the patient analysis populations.

Screened patients are defined as any patients who signed the informed consent.

Randomized patients consist of all patients with a signed informed consent form who have had a treatment kit number allocated and recorded in the IRT database, regardless of whether the treatment kit was used.

For patient study status, the total number of patients in each of the following categories will be presented in the clinical study report using a flowchart diagram or summary table:

- Screened patients
- Screen failure patients and reasons for screen failure
- Nonrandomized but treated patients
- Randomized patients
- Randomized but not treated patients
- Randomized and treated patients
- Patients who did not complete the 24-week treatment as per protocol
- Patients who did not complete the 52-week treatment as per protocol
- Patients who discontinued study treatment prior to Week 24 by main reason for permanent treatment discontinuation

- Patients who discontinued study treatment prior to Week 52 by main reason for permanent treatment discontinuation
- Patients who withdraw from study
- Patients who withdraw from study prior to Week 24
- Patients who withdraw from study prior to Week 24 by main reason for study discontinuation.
- Patients who withdraw from study prior to Week 52
- Patients who withdraw from study prior to Week 52 by main reason for study discontinuation.
- Patients who withdraw from study by main reason for study discontinuation
- Vital status at last study contact

For all categories of patients (except for the screened and nonrandomized categories) percentages will be calculated using the number of randomized patients as the denominator. Whether patients received rescue treatment (SCS or NP surgery) by Week 24 and Week 52 will be provided in tables. The tables will list patient numbers and percentages by treatment group and type of rescue treatment (SCS or NP surgery).

All critical or major deviations potentially impacting efficacy analyses, randomization, and drug-dispensing irregularities, and other major or critical deviations will be summarized in tables giving numbers and percentages of deviations by treatment group.

Additionally, efficacy populations will be summarized by number of patients on the randomized population.

- Efficacy population: intent-to-treat (ITT) population

The analysis populations for safety, pharmacokinetics/pharmacodynamics will be summarized by number of patents on the safety population.

- Safety population
- Systemic drug concentration population
- PK population
- ADA population
- Nasal biomarker substudy population

2.2.1 Randomization and drug dispensing irregularities

Randomization and drug-dispensing irregularities occur whenever:

1. A randomization is not in accordance with the protocol-defined randomization method, such as a) an ineligible patient is randomized, b) a patient is randomized based on an incorrect stratum, c) a patient is randomized twice, or d) in a dynamic randomization

scheme the treatment assignment is, in fact, not random, due to a computer program error.

OR

2. A patient is dispensed an IMP kit not allocated by the protocol-defined randomization, such as a) a patient at any time in the study is dispensed a different treatment kit than as randomized (which may or may not contain the correct-as-randomized IMP), or b) a nonrandomized patient is treated with IMP reserved for randomized patients.

Randomization and drug-dispensing irregularities will be monitored throughout the study and reviewed on an ongoing basis.

All randomization and drug-dispensing irregularities will be documented in the clinical study report. If the number of irregularities is large enough to make a tabular summary useful, the irregularities will be categorized and summarized among randomized patients (number and percentages). Nonrandomized, treated patients will be described separately.

Randomization and drug-dispensing irregularities to be prospectively identified include but are not limited to:

Randomization and drug allocation irregularities
Kit dispensation without IRT transaction
Erroneous kit dispensation
Kit not available
Randomization by error
Patient randomized twice
Forced randomization
Stratification error
Patient switched to another site

2.3 ANALYSIS POPULATIONS

Patients treated without being randomized will not be considered randomized and will not be included in any efficacy population.

The randomized population includes any patient who has been allocated to a randomized treatment regardless of whether the treatment kit was used.

For any patient randomized more than once, only the data associated with the first randomization will be used in any analysis population. The safety experience associated with any later randomization will be assessed separately.

2.3.1 Efficacy populations

The primary efficacy analysis population will be the ITT population as defined in [Section 2.3.1.1](#).

2.3.1.1 Intent-to-treat population

The intent-to-treat population is the randomized population analyzed according to the treatment group allocated by randomization.

Patients will be analyzed in the treatment group to which they are randomized.

2.3.2 Safety population

The safety population is defined as: All patients who actually received at least 1 dose or part of a dose of the IMP, analyzed according to the treatment patients actually received.

In addition:

- Nonrandomized but treated patients will be part of the safety population
- Randomized patients for whom it is unclear whether they took the IMP will be included in the safety population as randomized
- For patients on placebo but accidentally exposed to dupilumab, the treatment group allocation for as-treated analysis will be 300 mg q2w/q4w dose group (Arm B)
- For patients on dupilumab but accidentally receive different treatment from the planned, the actual treatment group allocation for as-treated analysis will be 300 mg q2w/q4w dose group (Arm B)

2.3.3 Pharmacokinetics (PK) population

The PK population will consist of all patients in the safety population with at least one evaluable functional dupilumab concentration result. Patients will be analyzed according to the treatment actually received.

2.3.4 Anti-drug antibody population

The anti-drug antibody (ADA) population will consist of all patients in the safety population with at least one reportable ADA results (either 'ADA negative' or 'ADA positive') after first dose of the study treatment. Patients will be analyzed according to the treatment actually received.

2.4 STATISTICAL METHODS

2.4.1 Demographics and baseline characteristics

Continuous data will be summarized using the number of available data, mean, standard deviation (SD), median, minimum, and maximum for each treatment group. Categorical and ordinal data will be summarized using the number and percentage of patients in each treatment group.

Parameters will be summarized on the randomized population analyzed in the treatment group to which they were randomized. Analyses for the safety population will be included in the appendices if the size of the safety population is different (>10%) from the size of that in the primary analysis population for any treatment group.

Parameters described in [Section 2.1.1](#) will be summarized by treatment group and overall treatment groups using descriptive statistics.

Medical and surgical history will be summarized by treatment group and by system organ class (SOC) and preferred term (PT) sorted by internationally agreed order of SOC and by the decreasing frequency of PT within SOC based on the overall incidence across treatment groups. Atopic medical history will be summarized separately.

No statistical testing on demographic and baseline characteristic data will be performed.

No specific description of the safety parameters will be provided at baseline. If relevant, the baseline values will be described along with each safety analysis.

2.4.2 Prior or concomitant medications

The prior and concomitant medications will be presented for the randomized population.

Medications will be summarized by treatment group according to the WHO-DD dictionary, considering the first digit of the anatomic category (ATC) class (anatomic category) and the first 3 digits of the ATC class (therapeutic category). All ATC codes corresponding to a medication will be summarized, and patients will be counted once in each ATC category (anatomic or therapeutic) linked to the medication. Therefore patients may be counted several times for the same medication.

The table for prior medications will be sorted by decreasing frequency of ATC followed by all other therapeutic classes based on the overall incidence across treatment groups. In case of equal frequency regarding ATCs (anatomic or therapeutic categories), alphabetical order will be used.

Concomitant medication received during first IMP to last IMP +14 days and concomitant medication received during first IMP to last IMP +98 days will be summarized separately. The tables for concomitant medications will be sorted by decreasing frequency of ATC followed by all

other therapeutic classes based on the incidence in the dupilumab 300 q2w group. In case of equal frequency regarding ATCs (anatomic or therapeutic categories), alphabetical order will be used.

Medications will also be summarized by generic name sorted by decreasing frequency based on the overall incidence across treatment groups.

In addition, MFNS controller medication will be summarized separately. Asthma controller medication(s) will also be summarized for asthma patients at baseline, Week 24 and Week 52 visits.

2.4.2.1 INCS/MFNS controller medication

INCS/MFNS controller medication taken within 1 year prior to screening will be summarized by treatment group sorted by decreasing frequency of generic name followed by total daily dosage based on the incidence in the overall group.

The prescription of INCS/MFNS controller medication at randomization will be summarized regarding QD and BID by treatment group.

2.4.2.1.1 Compliance

During the study, the daily intake of the INCS/MFNS controller medication will be recorded on the electronic diary every morning by patients as number of actuations. Compliance for INCS will be calculated for each patient. For each day, a patient is considered as compliant to the prescribed controller medication if the actual dose is the same as or greater than the prescribed dose (i.e. two actuations) for each nostril during each administration throughout the day: for one follows a QD (or BID) regimen, the patient is only considered as compliant to the prescribed INCS medication if the actual dose for each nostril administered during the day (or both in the morning and evening) is the same as or greater than the prescribed dose.

Percentage of Compliance is defined as the number of days when the patient is compliant to the prescribed controller medication divided by the number of days the patient stays in the treatment period (from first IMP to last IMP + 14 days).

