### 10.1 VISIT SCHEDULE

This section describes how the visits are carried out, in chronological order (according to the flow chart [Section 1.2](#) and identical to the order shown in the e-CRF):

The clinical trial consists of three periods, using an add-on therapy approach to INCS:

- Run-in Period (28 days+/- 3 days; V1).
- Randomized treatment period (up to 52 weeks +/- 3 days; Visits 2-10).
- Post-treatment Period (12 weeks; +/- 3 days V11).

The study visits occur on the planned dates (relative to the first injection), as scheduled. The visit schedule should be adhered to within the  $\pm 3$  day visit window.

If a patient is prematurely discontinued from treatment, every attempt should be made for the patient to return to the study site as soon as possible after last IMP administration to perform all assessments planned at the EOT visit and patients will be asked and encouraged to return to the study site for the visit scheduled as described in [Section 10.3.1](#) (early discontinuation) for a 12-week follow up.

Prior to all screening assessments, after discussion of participation in the study, the written consent form [REDACTED] must be signed and dated (see [Section 12.2](#)). At selected sites, requirements for collection of samples for a nasal biomarkers substudy will be included in a separate written informed consent.

Although the screening assessments for this study are grouped under the heading of a single visit in this protocol, it is possible for them to be performed over more than 1 site visit if necessary, as long as the run-in period window prior to Day 1 (V2) is respected. These patients do not need to sign a new consent form and be allocated a new patient number within this same window.

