### 10.3.1 Permanent treatment discontinuation with investigational medicinal product(s)

Permanent treatment discontinuation is any treatment discontinuation associated with the definitive decision from the Investigator or the patient not to re-expose the patient to the IMP at any time.

Patients who discontinue treatment permanently during the treatment period will be assessed as soon as possible using all procedures normally planned for the End-of-treatment Visit with the exception of CT Scan. Patients who discontinue early during the post-treatment period will be assessed as soon as possible using all procedures normally planned for the end-of-study (EOS) Visit.

For patients in whom the surgery date is scheduled after the planned end of study, a follow up contact(s) should be performed around the time of planned surgery to document the surgery date. Surgery data will be collected only until e-CRF Closure and EOS will not be delayed.

Patients will also be instructed to:

- Return to the study site for evaluations of NPS, SNOT-22, at:
  - Week 24, Week 52: If the ETD visit occurred between Week 0-Week 16,
  - Week 52: If the ETD visit occurred between >Week 16-Week 40,
  - Week 64 (EOS): If the ETD visit occurred between >Week 40-Week 52.
- Return and have a CT Scan performed as scheduled at Week 24 and 52.

Patients who discontinue prior to week 40 will have the following assessed through week 52, patients who discontinue after week 40 will have the following assessed through week 64:

- Perform PK and ADA sampling at the initially scheduled visits for these assessments
- Continue to complete the e-diary for nasal congestion, loss of smell daily symptom and anterior/posterior rhinorrhea evaluation
- Continue on MFNS stable dose but patients are not required to complete the INCS use daily in the e-diary after ETD.
- Advise patients with comorbid atopic conditions (such as asthma) not to adjust their treatment without consultation with their physicians.
- Report any AE up to the last scheduled visit (Week 52 or Week 64 depending on the discontinuation date).
- Contact the Investigator during the post treatment period up to the EOS visit if the symptoms worsen requiring medical attention.

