### **10.3.2 Temporary treatment discontinuation with investigational medicinal product(s)**

Temporary treatment discontinuation may be considered by the Investigator because of AEs. Re-initiation of treatment with the IMP will be made under close and appropriate clinical/and or laboratory monitoring once the Investigator will have considered according to his/her best medical judgment that the AE is sufficiently resolved and unlikely to recur after resuming therapy with IMP.

In addition, any of the following conditions will be a cause for temporary treatment discontinuation:

- Infections or infestations that do not respond to medical treatment should have study drug discontinued until the infection is resolved
- Any laboratory abnormality that meets temporary treatment discontinuation criteria as per [Appendix G](#).

For all temporary treatment discontinuations, duration should be recorded by the Investigator in the appropriate pages of the e-CRF. If the IMP is interrupted for more than 2 doses, then the patient should permanently discontinue the study treatment.

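### The MFNS compliance denominator can include days after the ETD visit, when the protocol no longer requires MFNS use to be recorded, so compliance is understated for some early stoppers

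*SAP*

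**What the plan says.** SAP 2.4.2.1.1 takes daily MFNS intake from the patient: it "will be recorded on the electronic diary every morning by patients as number of actuations". A day is compliant if the recorded dose reaches the prescribed dose for each nostril at each administration. The percentage for a patient is the count of such days, "divided by the number of days the patient stays in the treatment period (from first IMP to last IMP + 14 days"). The section gives no rule for a day without an entry.

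Protocol 10.3.1, on patients who permanently stop study drug, says: "Continue on MFNS stable dose but patients are not required to complete the INCS use daily in the e-diary after ETD". They do continue the diary for congestion, smell and rhinorrhea.

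On the timing of that visit, Protocol 10.1 asks that the patient "return to the study site as soon as possible after last IMP administration to perform all assessments planned at the EOT visit".

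**The concern.** The numerator needs a diary entry, while the denominator is calendar time. The two match as long as the patient is expected to record MFNS every day. After an early stop they can separate. The recording duty ends at the ETD visit, but the denominator runs on to 14 days after the last injection. If the visit comes first, the days in between are counted against the patient although the protocol has made the entry optional and the patient has been told to stay on the spray.

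At stake is how the background therapy is described. The primary objective is set on a background of MFNS, and this is the only MFNS compliance percentage that the SAP tabulates. For a patient who stops after a few injections, a low value could reflect data collection and not missed sprays.

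**Working it through.** The documents state no MFNS compliance figure, so there is none to reproduce. The check is direct arithmetic.

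**Inputs**
- Injections every 2 weeks, the last planned at Week 50 (Protocol 8.1.4). A full course is 26 injections, and an early stopper has k = 1 to 25.
- Denominator: first IMP to last IMP + 14 days (SAP 2.4.2.1.1). Counted as in the exposure formula of SAP 2.4.3.1, this is 14(k-1) + 14 = 14k days.
- g: days from the last injection to the ETD visit. The documents give no value, so it is varied from 0 to 14.
- Discontinuation share d: 25%, borrowed from the dropout allowance in SAP 1.3. Its use here, and the timing of stops, are assumptions.
- Full adherence to MFNS, a complete diary up to ETD, and no voluntary MFNS entries after it.

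**Per patient**

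Days with a required entry = 14(k-1) + g. Reported compliance = [14(k-1) + g]/(14k). Shortfall = (14-g)/(14k).

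| k | 14k | g = 0 | g = 3 | g = 7 | g = 14 |
|---|---|---|---|---|---|
| 1 | 14 | 0% | 21.4% | 50.0% | 100% |
| 3 | 42 | 66.7% | 73.8% | 83.3% | 100% |
| 4 | 56 | 75.0% | 80.4% | 87.5% | 100% |
| 12 | 168 | 91.7% | 93.5% | 95.8% | 100% |
| 25 | 350 | 96.0% | 96.9% | 98.0% | 100% |

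For example, k = 3 and g = 3 gives (28 + 3)/42 = 73.8%. At most 14 days per patient are involved. For a completer, 26 × 14 = 364 days, which ends at the Week 52 visit. No ETD visit applies and nothing is lost.

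**Arm mean**

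The SAP does not say how the percentage will be summarised. Taking the mean per arm, loss = d × (14-g)/14 × mean(1/k), with the last injection uniform over the stated range. Mean(1/k) is 0.1526 for k = 1 to 25 (stops spread over 52 weeks) and 0.2586 for k = 1 to 12 (all before Week 24).

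| g | d = 25%, over 52 weeks | d = 25%, all before Week 24 |
|---|---|---|
| 0 | 3.8 points | 6.5 points |
| 3 | 3.0 | 5.1 |
| 7 | 1.9 | 3.2 |
| 11 | 0.8 | 1.4 |
| 14 | 0 | 0 |

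For g = 7: 0.25 × 0.5 × 0.1526 = 1.9 points, and 0.25 × 0.5 × 0.2586 = 3.2 points. At d = 10% and g = 7 the losses are 0.8 and 1.3 points.

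**The case against.** The case on the other side is that this is a small matter in a descriptive table. Much of it stands.

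- **Recording is optional, not forbidden.** A reader might infer that patients are told to stop recording MFNS. The protocol says only that "patients are not required to complete the INCS use daily in the e-diary after ETD". A voluntary entry would count, so the shortfall above is an upper limit for a given g and k.
- **Short gaps are not assured.** The visit is due as soon as possible, but Protocol 10.3 makes permanent discontinuation a last resort. Protocol 10.3.2 adds: "If the IMP is interrupted for more than 2 doses, then the patient should permanently discontinue the study treatment". On that route the ETD visit falls after the 14-day tail and the effect is zero. A stop decided when the next injection is due also gives g of about 14 and no effect.
- **Other tracking exists.** Protocol 8.7.1 requires accountability for dispensed, returned, used and unused MFNS. The SAP plans no summary of it, so the tabulated percentage is still affected.
- **No inference depends on it.** Efficacy is analysed in the ITT population, MFNS compliance enters no model, and the SAP sets no on-treatment MFNS threshold.
- **Missing entries before ETD.** A reader might extend the point to every missing diary day. Crediting only documented full dosing while entries are still required is a conservative convention, and the run-in check at Visit 2 is also diary-based. It is not an error.

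None of this removes the mismatch for patients whose ETD visit does fall inside the tail.

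**Conclusion.** The point holds in a limited form. As written, the SAP understates MFNS compliance for early stoppers whose ETD visit comes less than 14 days after the last injection and who make no voluntary entries. The understatement is up to (14-g)/(14k) for a fully adherent patient: large after one or a few injections, and 2% to 4% at a 7-day gap after 12 to 25 injections.

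A reader might infer that reported MFNS compliance is too low in general. It is not: completers and patients with a later ETD visit are unaffected. A reader might also take 5 points as the expected arm-level effect. That figure needs a 3-day gap for every stopper and all 25% stopping before Week 24; the same share and gap spread over 52 weeks gives 3.0 points. At a 7-day gap the range is about 2 to 3 points. The share, timing and gap are all assumptions. A difference between arms would follow only if early discontinuation differed between them, which the documents do not establish.

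Severity is low. It concerns the description of background therapy, not a treatment comparison.

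**What to change.** In SAP 2.4.2.1.1, end the MFNS compliance denominator at the earlier of the ETD visit and last IMP + 14 days. A fully adherent early stopper with a complete diary up to ETD then returns to 100%, and completers do not change.

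Optionally, show beside it the percentage of those days with an MFNS diary entry, so that a reader can tell missing entries from missed sprays.

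The cost is one sentence in the SAP and, if wanted, one extra column in the table. No data collection, visit or treatment rule changes.
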